Study logs: We will use study logs to examine the number of potential participants screened, consented, and reasons for declining consent. Study clinicians will document the amount of time that they spend during BUP induction using the microdosing or TAU protocol following a check-list of steps.

Ecological momentary assessment (EMA): We will use EMA to examine opioid and pain-related symptoms (opioid withdrawal and craving, pain, anxiety), along with illicit opioid use, BUP dose taken, and pain treatments. Using smartphone mobile technology, participants will receive time-scheduled prompts to report symptoms, ecological conditions (e.g., current activities), and behaviors. We will record assessments in two periods: the first 2 weeks (induction) and 3-month follow-up. During induction, participants will report opioid- and pain-related symptoms at random times during 5 daily blocks. The relatively long period of data collection oriented to induction will allow EMA data collection in the hospital and after participants return home to resume normal activities. During follow-up, we will collect data during three additional 1-week “bursts” to complement data from in-person study visits. Bursts will be separated by at least 2 weeks and no more than 6 weeks over 3 months. Prompts will inquire about opioid- and pain-related symptoms, and context, such as physical activity, which may affect these symptoms and OUD or pain outcomes. As with our current studies, research staff will assist in downloading the secure customized EMA technology (www.llumivu.com) onto participant smart phones, and provide training to use the technology.¹⁰⁶ Participants without smart phones will be provided one. Each report will take 1-2 minutes to complete. Based on the lack of significant reactivity effects found in past research, 5 standard EMA random reports will be prompted daily.^{117,118} EMA measures are summarized in **Table E-4**.

Adherence to EMA: Participants will receive \$0.20 for each set of assessments completed. If they complete more than 90% of assessments weekly, they will receive a bonus of \$10. Feedback regarding EMA adherence will be provided with reminders about compensation. Total compensation can be \$17 per EMA week.

E.2.10 Key Outcomes for Aims 1 and 2:

The **primary outcome** will be **BUP uptake**, defined as receiving BUP 7 days after the baseline visit using EHR data on hospital medication administration or prescription (dichotomous, yes/no).

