H₁: *The microdosing arm (vs. TAU) will have better BUP treatment uptake and retention, and less illicit opioid use.* Our primary analysis will be a logistic regression comparing the proportion of participants in each study arm who meet our definition of BUP uptake (see D.2.10). Secondary analyses will examine BUP retention and illicit opioid use as secondary outcomes. We will use a mixed effects logistic regression model to examine BUP retention at 1, 3, and 6 months and a mixed effects linear regression model to examine number of days of illicit opioid use (over 30 days) at 1, 3, and 6 months. Study arm will be considered a fixed effect, and participant and time (months) will be considered random effects. Additional analyses will include key variables mentioned above as covariates and potential confounders if they differ by study arm.

H₂: *Improvements in H₁ will be mediated by opioid- and pain-related symptoms.* Based on the model

described in **Figure E-3**, we will use structural equation modeling to determine whether improvements in OUD outcomes are due to improvements in opioid- and pain-related symptoms. We will use EMA data (5 random reports per day) and data from in-person visits at baseline, 1 week, 1, 3, and 6 months. For example, when the dependent variable is BUP uptake, we will calculate the standardized total effect from the intervention (BUP microdosing) to BUP uptake, as well as the standardized mediational (i.e., indirect) effect of opioid- and pain-related symptoms (e.g., withdrawal). The mediational effect is calculated as the product of the effect from intervention to the mediator, and the effect from the mediator to the outcome. To account for the influence of the baseline measures (e.g., sociodemographic characteristics) on the outcome and the mediator, we will use a partial correlation matrix as the input matrix. This will be created by statistically parsing out the effects of the baseline measures cited above on the mediator and the outcome variable. Our proposed model will be estimated using Mplus.¹³⁰ Overall model fit will be assessed by: (1) the root mean

[figure not shown]

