effect of opioid- and pain-related symptoms (e.g., withdrawal). The mediational effect is calculated as the product of the effect from intervention to the mediator, and the effect from the mediator to the outcome. To account for the influence of the baseline measures (e.g., sociodemographic characteristics) on the outcome and the mediator, we will use a partial correlation matrix as the input matrix. This will be created by statistically parsing out the effects of the baseline measures cited above on the mediator and the outcome variable. Our proposed model will be estimated using Mplus.¹³⁰ Overall model fit will be assessed by: (1) the root mean

square error of approximation (RMSEA), (2) Bentler's comparative fit index (CFI),¹³¹ and (3) the standardized root mean square residual (SRMR). To account for non-normal distribution of the model variables (e.g., BUP uptake), we will use Mplus's maximum likelihood with robust standard errors (MLR) as the estimator.

Aim 2: To test the effectiveness of microdosing (vs. TAU) on pain outcomes.

H₃: The microdosing arm (vs. TAU) will have less pain intensity and interference, and improved quality of life. We will use separate mixed effects linear regression models to compare each pain outcome from baseline to 3 months. Main analyses will use data from in-person visits at baseline, 1 week, 1 and 3 months. Study arm will be considered a fixed effect, and participant and time will be considered random effects. In additional analyses, we will include key variables mentioned above as covariates and potential confounders if they differ by study arm. We will also examine sustainability of outcomes at 6 months.

H₄: Improvements in H₃ will be mediated by OUD outcomes. Based on the model described in **Figure E-4**

and similar to the analyses for H2 (see above), we will use structural equation modeling to determine whether improvements in pain outcomes are due to improvements in OUD outcomes. For example, when the dependent variable is pain intensity, we will calculate the standardized total effect from the intervention (BUP microdosing) to pain reduction at 3 months, as well as the standardized mediational (i.e., indirect) effect of BUP uptake, BUP retention, and illicit opioid use. For these analyses, our primary mediator is BUP retention. We will use both the EMA data (5 random reports per day) and data from in-person visits at baseline, 1 week, 1 and 3 months.

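### The H2 and H4 mediation models specify both a correlation-matrix input and robust (MLR) standard errors, which cannot be combined; fit individual records and state the scale for binary uptake and retention

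*Combined protocol and SAP*

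**What the plan says.** All references are to the combined protocol and SAP.

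- **Input (D.2.11, H2).** The plan adjusts the structural equation model for baseline measures through its input: "we will use a partial correlation matrix as the input matrix". On how the matrix is built: "This will be created by statistically parsing out the effects of the baseline measures cited above on the mediator and the outcome variable".
- **Estimator (D.2.11, H2).** A few sentences later: "we will use Mplus's maximum likelihood with robust standard errors (MLR) as the estimator". The reason given is non-normality of the model variables, with BUP uptake as the example.
- **Outcome in the model (D.2.11, H2).** In the plan's own example, "when the dependent variable is BUP uptake, we will calculate the standardized total effect from the intervention (BUP microdosing) to BUP uptake". The indirect effect is the product of the arm-to-mediator and mediator-to-outcome effects.
- **Scale of uptake.** The key outcomes section defines uptake as dichotomous. For H1 the plan treats it as such: "Our primary analysis will be a logistic regression comparing the proportion of participants in each study arm". Retention, also yes/no at each time point, gets a mixed effects logistic model under H1.
- **H4 (D.2.11).** The method is to be similar to H2: "we will use structural equation modeling to determine whether improvements in pain outcomes are due to improvements in OUD outcomes". Retention is the primary mediator.

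The mediation text names no link function, no categorical-outcome estimator and no special correlation for binary variables. It does not say that the model will be fitted to individual or residualised records.

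**The concern.** A robust (sandwich) variance is assembled from each participant's contribution to the likelihood. Once the data are reduced to a correlation matrix, those contributions are gone. An analyst who follows the input instruction can obtain only normal-theory standard errors. An analyst who follows the estimator instruction has to set the matrix aside. The plan does not say which instruction gives way.

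This matters because MLR is the plan's stated answer to having a yes/no variable in the model. If the matrix is kept, that answer is lost. Every indirect effect under H2 and H4, two of the five named hypotheses, rests on this model. The same text also leaves unstated whether uptake and retention are modelled linearly or through a link, and so on what scale an indirect effect would be reported.

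**Working it through.** The documents give no sample size, power or standard error for the mediation models, so there is no planned figure to reproduce. Two checks were made.

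**Check A: does the matrix determine the robust standard error?**

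Take arm X, mediator M and outcome Y, standardised, with n = 270 (135 per arm, D.2.12). The documents give no correlations, so these are assumed: r(X,M) = −0.30, r(X,Y) = 0.374, r(M,Y) = −0.35. The value 0.374 is the correlation implied by the plan's uptake figures of 61% and 24%: 0.37 × 0.5 / √(0.425 × 0.575) = 0.374. Baseline measures are left out for simplicity; partialling them out still leaves second moments only.

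1. Arm to mediator: a = −0.30.
2. Mediator to outcome given arm: b = (−0.35 − (−0.30)(0.374)) / (1 − 0.09) = −0.2378 / 0.91 = −0.2613.
3. Indirect effect: ab = 0.0784.
4. Normal-theory SE of a: √(0.91 / 270) = 0.0581.
5. Normal-theory SE of b. The direct path is (0.374 − 0.105) / 0.91 = 0.2956. R² = 0.2956 × 0.374 + 0.2613 × 0.35 = 0.202. SE = √(0.798 / (270 × 0.91)) = 0.0570.
6. Normal-theory SE of ab: √(a² SE_b² + b² SE_a²) = √(0.09 × 0.0570² + 0.2613² × 0.0581²) = 0.0229.

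Steps 1 to 6 use only the matrix and n. The robust variance of b is Σ m̃ᵢ² eᵢ² / (Σ m̃ᵢ²)², where m̃ᵢ is the mediator residual given arm and eᵢ the outcome residual. Its numerator is a fourth-order sum over participants and cannot be obtained from the matrix.

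To see the effect, three data sets of 270 records were built with exactly this matrix. They differ only in how the scatter of Y varies with M.

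| Data set | ab | Normal-theory SE(ab) | Robust SE(b) | Robust SE(ab) |
|---|---|---|---|---|
| Constant scatter | 0.0784 | 0.0229 | 0.0643 | 0.0245 |
| Scatter grows away from mean M | 0.0784 | 0.0229 | 0.1104 | 0.0364 |
| Scatter shrinks away from mean M | 0.0784 | 0.0229 | 0.0315 | 0.0179 |

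One matrix is compatible with robust standard errors that differ by a factor of 0.0364 / 0.0179 = 2.0.

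**Check B: what happens with binary uptake on individual records?**

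Uptake was simulated at 24% and 61% with n = 270 and 1,000 replicates. Assumptions: the arm shifts the mediator by −0.5 SD, and the log-odds of uptake change by −0.5, −1.0 or −1.5 per SD of mediator. Uptake was fitted as a linear outcome; the figures are for the mediator-to-uptake path.

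| Log-odds slope | True sampling SD | Robust SE | Normal-theory SE | Normal-theory SE / true SD | Fitted values outside 0–1 |
|---|---|---|---|---|---|
| −0.5 | 0.0277 | 0.0263 | 0.0273 | 0.99 | 0.8% |
| −1.0 | 0.0232 | 0.0235 | 0.0257 | 1.11 | 5.5% |
| −1.5 | 0.0207 | 0.0211 | 0.0243 | 1.17 | 9.9% |

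With individual records the robust error follows the true sampling variation. It corrects the variance only; the straight-line model for a probability remains, as the last column shows.

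**The case against.** The best defence is that the inconsistency is loose wording. The trial will hold individual records. Removing baseline effects from mediator and outcome at record level gives residualised records, and MLR can be run on those. This is right as far as it goes, so a reader who infers that the mediation analysis cannot be done at all goes too far. But the plan does not describe this route; it names the matrix as the input. The route also fits only a linear treatment of uptake, because a residualised 0/1 variable is no longer 0/1.

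Other stronger readings are tempting, and the documents do not support them:

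- **The analyst would have to choose after seeing the data.** The conflict is visible from the text and can be settled before any outcome is examined.
- **Missing data cannot be handled.** D.2.11 plans multiple imputation with five imputations for Aims 1 and 2, which include H2 and H4.
- **EMA reports cannot be represented.** They could enter as participant-level or burst-level summaries. The plan does not say which, but an unstated summary is not an impossible one. The model diagrams (Figures E-3 and E-4) are not in the copy reviewed.
- **A linear model for uptake is wrong.** With individual records and robust errors it is defensible on the risk-difference scale, and check B supports this. Even the normal-theory error was about right to mildly conservative there (0.99 to 1.17 times the true SD).
- **A categorical link and bootstrap intervals are required.** They are options. Under a logit or probit link the product of coefficients is not in general the indirect effect on the probability scale, so the plan's definition would have to change.

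What remains untouched is the core: a correlation matrix alone cannot yield the robust standard errors that the plan specifies.

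**Conclusion.** The point holds in this limited form. The matrix input and MLR, both specified for H2 and carried into H4, cannot be applied together. Following the matrix instruction leaves normal-theory errors and gives up the stated protection for a yes/no variable. The scale for binary uptake and retention is also unstated.

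The conflict reaches all H2 and H4 indirect effects that involve non-normal variables. Its numerical consequence in this trial cannot be computed from the documents. The two-fold spread in check A comes from constructed data with assumed correlations and proves only that the matrix does not determine the error. Check B, under its assumed mediator effects, suggests a modest distortion on one path. The conclusion about incompatibility depends on neither set of assumptions.

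A reader might infer that the main result is at risk. It is not: the primary logistic comparison, the H1 and H3 mixed models and the sample size do not use this model.

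**What to change.** Amend the H2 text in D.2.11, and let H4 refer to it:

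1. Delete the partial-correlation-matrix step. Fit the model to individual-level records with MLR, in each imputed data set.
2. Enter the pre-randomisation baseline measures as predictors of mediator and outcome, instead of removing their effects beforehand.
3. State the scale for uptake and retention. Either use a linear (risk-difference) model with robust errors, which keeps the product-of-coefficients definition, or use a categorical link with the total and indirect effects defined to match.
4. If wanted, name bootstrap intervals for the indirect effects. This is optional.

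The cost is a wording change before analysis. It needs no new data, no additional participants and no change to the primary analysis.

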We propose to test BUP microdosing vs. treatment as usual (TAU), meaning standard BUP induction. We will conduct a hybrid type 1 effectiveness-implementation study, using a pragmatic, open-label, randomized controlled trial (RCT). We will randomize 270 hospitalized patients with (a) CP and (b) opioid misuse or OUD to a 4-day microdosing protocol (without stopping full agonists) or 2-day standard induction (with stopping full agonists), and link them to outpatient BUP treatment. Study assessment visits will occur at baseline, 1 week, and 1, 3, and 6 months. The primary outcome will be BUP treatment uptake (taking BUP 7 days after baseline). Secondary OUD outcomes will be illicit opioid use and retention in care at 1, 3, and 6 months. Secondary pain outcomes will be pain intensity, pain interference, and quality of life at 3 months. Changes in pain and quality of life will be mediated by BUP treatment uptake and retention. During induction and 3-months of follow-up, we will also collect data for Ecological Momentary Assessment (EMA) of opioid withdrawal, craving, pain, and anxiety ("opioid- and pain-related symptoms"). These EMA data will allow us to assess whether BUP microdosing's targets of engagement—opioid- and pain-related symptoms—mediate OUD outcomes. Exploratory analyses will also examine pain as a trigger for opioid relapse.

Aim 1: To test the effectiveness of microdosing (vs. TAU) on OUD outcomes.

***H₁:* The microdosing arm (vs. TAU) will have better BUP treatment uptake and retention, and less illicit opioid use. *H₂:* Improvements in H₁ will be mediated by opioid- and pain-related symptoms.**

Aim 2: To test the effectiveness of microdosing (vs. TAU) on pain outcomes.

***H₃:* The microdosing arm (vs. TAU) will have less pain intensity and interference, and improved quality of life. *H₄:* Improvements in H₃ will be mediated by OUD outcomes.**

Aim 3: To inform future implementation and dissemination efforts, we will: 3a) Examine factors influencing reach, adoption, implementation, and maintenance of BUP microdosing. We will use qualitative and quantitative methods to describe multi-level factors influencing these domains; **3b) Calculate**

the cost and examine cost-effectiveness of BUP microdosing. H_5 : Compared with TAU, BUP microdosing will be cost-effective from a societal and a health sector perspective.

[figure not shown]
B. SIGNIFICANCE

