Secondary OUD outcomes include illicit opioid use and BUP retention. **Illicit opioid use** will be examined as the number of days of illicit opioid use (defined as self-reported use of heroin, fentanyl, or non-prescribed opioid analgesics) in the prior 30 days based on the Addiction Severity Index (continuous).¹¹⁹ Because urine drug testing (UDT) only captures opioid use in the prior 24-72 hours, it is a less sensitive measure of substance use over time; however, UDT results will be a secondary outcome measure. **BUP retention** will be

Table E-4. Ecological Momentary Assessment (EMA) Measures

Construct	Measure
EMA opioid- and pain-related symptoms	
Opioid withdrawal	Subjective Opioid Withdrawal Scale (SOWS)
Opioid craving	Visual analog scale
Pain intensity	Adapted BPI pain severity subscale
Anxiety	Generalized Anxiety Disorder-7 (GAD-7)
Exploratory EMA outcomes	
Illicit opioid use	Self-report
BUP dose	Self-report
Pain treatment	Self-report

*All measures will occur at bursts 1 & 2 weeks, and 1, 2, & 3 months

defined as having a BUP prescription written the following number of days after baseline: 30-60 days (1-month retention); 90-120 days (3-month retention); and 180-210 days (6-month retention). To be retained at 3 and 6-months, participants will be required to have been retained at previous time points.⁴⁶ All OUD outcomes are consistent with elements of the Opioid Use Disorder Cascade of Care.¹²⁰

Secondary pain outcomes include pain intensity, pain interference, and quality of life. *Pain intensity* will be measured using the Brief Pain Inventory (BPI).¹²¹ We will use the mean of 4 items that assess pain intensity over the past 24 hours on a scale of 1-10 (1=minimal pain, 10=intense pain). We will use the mean of these 4 items. *Pain interference* will be measured using the pain interference scale from the BPI, which is a 7-item instrument measuring the impact of pain on daily activities and physical functioning. It is rated on a scale of 1-10 (1=minimal interference, 10=high interference). We will use the mean of these 7 items. *Quality of life* will be measured using the PROMIS-Preference Scoring System (PROP-Pr), which is described in detail as part of the cost-effectiveness analyses below (see D.4.1).¹²²⁻¹²⁴ In our main analyses, we will examine changes from baseline to 3 months for all pain outcomes; in additional analyses, we will examine sustainability at 6 months.

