Sex as a biological variable. For Aims 1 and 2, we will examine sex as a biological variable by conducting stratified analyses by sex. In addition, we will conduct exploratory analyses to test whether there is a two-way interaction between OUD and pain outcomes and sex.

Exploratory analysis: E₁: During induction, opioid withdrawal and pain will be lower in the microdosing (vs. TAU) arm. We will use EMA data (5 random reports per day: within-individuals, repeated data) to examine if those in the microdosing arm report less opioid withdrawal and pain. Multilevel models will be used where random reports that record changes in opioid withdrawal and pain are assessed within individuals (level 1), and study arm is assessed between individuals (level 2). For example, study arm (level 2: microdosing vs. TAU) will be regressed onto opioid withdrawal (level 1). A significant coefficient for study arm indicates significant differences in overall levels of opioid withdrawal across study arms. We will also describe daily changes (linear or curvilinear) in opioid withdrawal and pain over time by including time (days since the beginning of induction) in the models above. Subsequently, a treatment x time interaction term will be included in models to examine if the trajectory (rates of changes over time) of opioid withdrawal and pain differ across study arms. Separate models will examine opioid withdrawal and pain, and separate models will examine induction (weeks 1, 2) and follow-up (1, 2, 3 months).

E₂: Increases in pain intensity will be associated with illicit opioid use in follow-up. We will use EMA data (5 random reports per day: the within-individuals, repeated data) to examine whether increases in pain are associated with illicit opioid use during the follow-up period (three 1-week bursts). We will use multilevel models to prospectively examine whether pain level at time 1 (T1) predicts illicit self-reported opioid use between T1 & T2, controlling for the previous pain level (T0), age, sex, and use of other pain treatments. In addition, we will include a pain x BUP initiation interaction term to test whether the relationships between pain and subsequent illicit opioid use differ across participants who do and do not initiate BUP treatment.

D.2.12 Power and Sample Size: We will power the study based on the primary outcome of BUP uptake. We plan to enroll 135 participants in each arm. While published case studies report high levels of success with

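### The H3 pain model names only study arm as a fixed effect, so its arm coefficient averages over visits instead of estimating the 3-month effect the plan targets

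*Combined protocol and SAP*

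**What the plan says.** The time point is set in three places.

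- Section A, Specific Aims: "Secondary pain outcomes will be pain intensity, pain interference, and quality of life at 3 months".
- Key Outcomes for Aims 1 and 2 (numbered E.2.10), on the main analyses: "we will examine changes from baseline to 3 months for all pain outcomes".
- D.2.12: the pain power calculation rests on the change in pain intensity over the same interval.

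The H3 model is in D.2.11, Aim 2: "We will use separate mixed effects linear regression models to compare each pain outcome from baseline to 3 months". On data: "Main analyses will use data from in-person visits at baseline, 1 week, 1 and 3 months". On structure: "Study arm will be considered a fixed effect, and participant and time will be considered random effects". The additional analyses bring in covariates, and then: "We will also examine sustainability of outcomes at 6 months". No contrast is named for either time point.

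Exploratory analysis E1, also in D.2.11, is more explicit about a repeated-measures model. It interprets the arm term this way: "A significant coefficient for study arm indicates significant differences in overall levels of opioid withdrawal across study arms". To study trajectories it adds a further term: "Subsequently, a treatment x time interaction term will be included in models". H3 has no such term.

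**The concern.** With arm as the only named fixed effect, the model holds one arm parameter, and that parameter pools the arm difference over all visits in the response. E1 reads the same kind of coefficient as a difference in overall level. The stated target is the difference at one visit.

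Two readings of the response are open. If baseline is a response row, the average includes a visit at which randomisation makes the expected difference zero. If the response is change from baseline, the average still covers 1 week, 1 month and 3 months. Quality of life has no 1-week assessment in Table E-3, so its coefficient averages over a different set of visits from the two BPI outcomes.

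The H3 test could therefore miss an effect that builds up towards 3 months, or declare one that has disappeared by then. The 80% power in D.2.12 belongs to a contrast the model does not name.

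**Working it through.** **Inputs from D.2.12:** 135 per arm; SD of pain intensity 1.6 and mean 7.3 at baseline; SD of change 1.8; d = 0.34 at 80% power.

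**Assumed:** two-sided 0.05, the same SD at each visit, compound symmetry, complete data, normal-approximation power, and the time course of the effect, which the documents do not give.

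**1. The plan's own figure.** d = (1.960 + 0.842) × √(2/135) = 0.341, which matches 0.34. In points, 0.34 × 1.8 = 0.612, and 0.612/7.3 = 8.4%, also as stated. The figure is sound for a comparison of 3-month change.

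**2. Implied correlation.** ρ = 1 − 1.8²/(2 × 1.6²) = 0.367.

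**3. Standard errors of the arm difference, n = 135 per arm.**

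- Mean of four visits: 1.6 × √((1 + 3ρ)/4) × √(2/n) = 0.141
- Mean of three changes: 1.6 × √((1 + 2ρ)/3 + 1 − 2ρ) × √(2/n) = 0.179
- Change at 3 months: 1.8 × √(2/n) = 0.219
- Baseline-adjusted 3-month difference: 1.6 × √(1 − ρ²) × √(2/n) = 0.181

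**4. What the arm coefficient estimates.** On balanced data it is the equal-weight mean of the visit differences. A random intercept for visit leaves the four weights at 0.25 each. The true 3-month difference is 0.612 in the first three rows and zero in the last; the linear pattern uses days 7, 30 and 90.

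| Effect pattern | Baseline in response: coefficient (share of 0.612) | Power | Change as response: coefficient (share of 0.612) | Power |
|---|---|---|---|---|
| Constant from week 1 | 0.459 (75%) | 90% | 0.612 (100%) | 93% |
| Linear in time | 0.216 (35%) | 33% | 0.288 (47%) | 36% |
| Only at 3 months | 0.153 (25%) | 19% | 0.204 (33%) | 21% |
| 0.612 at 1 week and 1 month, zero at 3 months | 0.306 (50%) | 58% | 0.408 (67%) | 63% |

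In the last row the percentage is the chance of a significant result when the 3-month effect is zero.

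**5. Comparators that target 3 months.** In the first three patterns a direct comparison of 3-month change has 80% power (0.612/0.219 = 2.79), and the baseline-adjusted 3-month contrast has 92% (0.612/0.181 = 3.38).

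**6. Sensitivity.** The shares do not depend on ρ, but power does. For ρ from 0.2 to 0.7:

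- With baseline in the response, power falls from 96% to 76% (constant) and from 42% to 24% (linear).
- With change as the response, power rises from 86% to 99.9% (constant) and from 30% to 65% (linear).

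With 113 complete cases per arm (0.84 × 135 = 113.4, borrowing the 6-month retention quoted in D.2.6), the first three patterns give 84%, 29% and 17% with baseline in the response, and 88%, 31% and 18% with change. The comparators become 72% and 87%, and the vanished effect is declared 51% or 55% of the time.

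None of these figures models the remark in D.2.12 that pain reduction is considered only for participants with BUP uptake.

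**The case against.** The strongest reply is that this is under-specification, not a wrong test. The Key Outcomes section says the main pain analyses examine change, so change is the natural response, and listing baseline among the visits may only mean that it is needed to compute change. Calling arm a fixed effect does not say it is the only one. H3 itself carries no time point, and comparing outcomes from baseline to 3 months could mean over that period. An analyst who follows the Key Outcomes section could add the 3-month comparison without breaking the plan.

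Part of this stands. The change reading is the better supported, and the less favourable column of the table belongs to the other one. But the change reading still averages three visits, so it matches the target only if the effect is constant from week 1. And if the arm main effect, an interaction and a change-score comparison all comply, the choice of H3 test is left open until after the data are seen, in an open-label trial.

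It is also fair that the shares depend on how random time is read. Under a participant-level random slope with assumed SDs of 0.2 to 0.6 points per month, and baseline in the response, the 3-month visit gets a weight of about 0.21 down to 0.05. The coefficient is still an average, with even less weight on the target visit. The shares of 75%, 35% and 25% are not general.

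Finally, the time courses are assumed, and a constant effect is detected with more power than the direct comparison of 3-month change has. Both points are correct and limit the claim.

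**Conclusion.** The concern holds. The documents consistently target pain at 3 months, and the model given for H3 estimates something else unless the response is change and the effect is constant over visits. That mismatch needs no assumed number.

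Its size does depend on assumptions: equal SDs, compound symmetry at ρ = 0.367, complete data and an invented time course. Under them the coefficient ranges from a quarter of the 3-month effect to all of it. This is not a general loss of power, and the d of 0.34 is not in error; it simply belongs to another contrast.

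The primary uptake analysis is untouched. Because H3 is the main test of Aim 2, this should be fixed before analysis.

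**What to change.** In D.2.11, Aim 2, state whether the response is level or change, name the baseline-adjusted arm contrast at 3 months as the H3 test for each pain outcome, and name the arm contrast at 6 months as the sustainability analysis.

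One suitable model is a repeated-measures model with categorical visit, arm-by-visit terms, and baseline either as a covariate or through a common baseline mean; for quality of life the post-baseline visits up to the H3 time point are 1 and 3 months only. A baseline-adjusted comparison at 3 months alone would also meet the target.

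The cost is a few sentences of SAP wording. The data and software stay the same.
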